- Step 2 (optional): Explore adding other covariate terms to the Step 1 model (for example, but not limited to, Age, Gender, Dose per kg, Blood eosinophil levels). Use expert judgment and changes in DIC to determine final model to take to Step 3. Include any Step 2 models in the listing output and add the associated DIC / changes in DIC values to those produced in Step 1.
- Step 3: For the finally selected model use appropriate combinations of the model parameters (back transforming the combination if necessary) to obtain posterior distributions for the quantities of interest described in the Model Results Presentation. Binary flag variables can be used to evaluate the probability statements, by tracking the instances of the desired event happening over each MCMC iteration and taking the mean of the flag variable as the probability.

For example, if Model 3 is selected then the posterior distribution for the Placebo can be

Primary Statistical Analyses

obtained from adding model parameters Intercept + Treatment[#1] Note: The baseline term is centered and drops out of the expression since it is evaluated at its centered mean of zero; similarly the random centre effect also has mean zero.

The treatment difference (Active – Placebo) would be –Treatment[#1] because the Treatment[#2] parameter is constrained to be zero and the other model terms cancel out.

The Percentage attenuation would be $100 * (1 - (\text{Intercept} / (\text{Intercept} + \text{Treatment}[\#1])))$

The SAS syntax for setting up indicator flags to obtain the probability of any percentage attenuation is Myflag = (pctann > 0); where pctann is the variable storing the Percentage attenuation.

Programming technical note(s): i) Use of flag variables may result in several error/warning messages in the SAS log (for example, but not limited to, warnings about large autocorrelation and/or zero variance); which should be reviewed but may be safely discounted – if in doubt consult the study statistician. ii) To facilitate summary outputs where results from multiple models are displayed simultaneously (large) intermediate datasets from Proc MCMC may need to be stored to ensure consistency (i.e. no differences due to simulation error between model re-runs). Suitable naming conventions should be used to label these files which group related items together.

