- Assuming that the final model is not of the “R1” form (See Section [11.9.1](#)) then treatment comparisons of interest are the equivalents to the frequentist counterpart LSMeans estimates for Treatment*Visit in a model fitted in SAS PROC MIXED. The posterior distributions of these quantities will be obtained and the median and 95% credible interval (equi-tail) will be tabulated and displayed graphically. Additionally, appropriate combinations of model parameters will be constructed to obtain the posterior distributions of the ratio of Active / Placebo for each planned time point (equivalent to extracting out relevant back transformed LSmean diffs from a PROC MIXED call for a log-transformed response variable). The posterior probabilities that the ratios at each planned timepoint exceeded the cut-points described [Table 14](#) will be computed, along with the median and 95% credible interval (equi-tail) of the distribution. The posterior distributions for the ratios will be displayed graphically and the aforementioned items tabulated. Note: These posterior probabilities relate to events in the current study, and the mean responses on the treatment arms. Predictions relating to i) an individual subject in a future trial and ii) the mean response in a future trial with N subjects per arm will not be produced as part of the reporting of this study, but may be obtained as part of experimental design activities for any future clinical trials involving GSK22454035.
- If the model is of the “R1” form (See Section [11.9.1](#)) then the approach will be modified to obtain and display LSMean equivalents of Treatment*Visit*Allergen and the comparisons would be the ratio of Active/Placebo within each Allergen strata within each visit. The same set of default posterior probability cut points will be used for each comparison.

Pharmacodynamic/Biomarker

Table 14 Default Posterior Probability (PP) cut-points of interest for Pharmacodynamic/Biomarkers analyses

Item	X = Treatment ratio (Active / Placebo) at each planned time point
1	PP(X<0.10) "More than a 90% reduction in mean response relative to Placebo"
2	PP(X<0.25) "More than a 75% reduction in mean response relative to Placebo"
3	PP(X<0.50) "More than a 50% reduction in mean response relative to Placebo"
4	PP(X<0.75) "More than a 25% reduction in mean response relative to Placebo"
5	PP(X<0.90) "More than a 10% reduction in mean response relative to Placebo"

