6	PP(X<1.00) "Any reduction in mean response relative to Placebo"
7	PP(X≥1.00) "Any increase in mean response relative to Placebo"
8	PP(X>1.10) "More than a 10% increase in mean response relative to Placebo"
9	PP(X>1.25) "More than a 25% increase in mean response relative to Placebo"
10	PP(X>1.50) "More than a 50% increase in mean response relative to Placebo"
11	PP(X>2.00) "More than a 2-fold increase in mean response relative to Placebo"
12	PP(X>10) "More than a 10-fold increase in mean response relative to Placebo"
Note: If the response is untransformed then the cut-points will be computed using the median of the posterior (adjusted) distribution for Placebo and the above ratios to determine the equivalent absolute difference (e.g. If Pbo median = 76 then Item 1 would be PP(Difference (A-P) < -68.4))	
Note: Shortened versions of the labels may be used in the TLFs as appropriate (e.g. PP(X<0.10) or PP(Any Reduction c.f. Pbo))	

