9 EXPLORATORY STATISTICAL ANALYSES

9.1 Exploratory Analyses

9.1.1 Overview of Planned Exploratory Analyses

The exploratory analyses will be based on different populations depending on what the endpoint is.

Table 16 provides an overview of the planned exploratory analyses, with further details of data displays being presented in [Appendix 13: List of Data Displays](#).

Table 16 Overview of Planned Exploratory Analyses

Endpoint	Absolute							
	Stats Analysis			Summary		Individual		
	T	F	L	T	F	F	L	
TNSS								
WM TNSS by Week	Y		Y		Y		Y	
WM Individual Components of TNSS by Week	C		C		C		C	

NOTES :

- T = Table, F = Figure, L = Listing, Y = Yes display generated, C=Display conditional on other results.
- Stats Analysis = Represents TFL related to any formal statistical analyses (i.e. modelling) conducted.
- Summary = Represents TFL related to any summaries (i.e. descriptive statistics) of the observed raw data.
- Individual = Represents FL related to any displays of individual subject observed raw data.

Intradermal Allergen Challenge	Log Untransformed											
	Absolute						Change from Baseline					
	Stats Analysis			Summary		Individual	Stats Analysis			Summary		Individual
	T	F	L	T	F	F	L	T	F	L	T	F
Mean Diameter Early Phase Response (15m)												
Wheal/Flare data	C	C	C	Y			Y			Y	Y	Y
Mean Diameter Late Phase Response (6h)												
Wheal/Flare data	C	C	C	Y			Y			Y	Y	Y

NOTES :

- T = Table, F = Figure, L = Listing, Y = Yes display generated, C=Display conditional on other results.
- Stats Analysis = Represents TFL related to any formal statistical analyses (i.e. modelling) conducted.
- Summary = Represents TFL related to any summaries (descriptive statistics) of the observed raw data.
- Individual = Represents FL related to any displays of individual subject observed raw data.

Weighted Mean TNSS

The weighted means of the TNSS values (AM and PM values combined into an overall daily score prior to deriving WM) will be derived for each diary card week. They will be analysed using a similar model to FeNO (Section [8.4.2.3.5](#)) except the response is not anticipated to require any transformation, so the model should be modified to examine differences and not ratios and to account for the additional Follow Up Visit timepoints.

Baseline would be the Day 1 AM TNSS value and Visit would be the week (of each weighted mean).

Conditional on the above output the following may be attempted (and would be assigned the next available output number):

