11.13.13 Exploratory Tables

Exploratory: Tables					
No.	Population	IDSL / TST ID / Example Shell	Title	Programming Notes	Deliverable [Priority]
TNSS					
6.1.	All Subjects	EFF_T1	Summary Statistics of Weighted Mean TNSS by Week	Separate Tables within the output for Overall TNSS and the AM and PM WM endpoints	FSP: SAC 2
6.2.	All Subjects	EFF_T2	WM TNSS: Summary of Posterior Distributions and Posterior Probability statements from the Analysis of Weekly WM TNSS data		FSP: SAC [2]
6.3.	All Subjects	EFF_T1	Summary Statistics of TNSS component Weighted Means by Week	Conditional	FSP: SAC 2
6.4.	All Subjects	EFF_T2	WM TNSS: Summary of Posterior Distributions and Posterior Probability statements from the Analysis of Weekly WM TNSS component data	Conditional	FSP: SAC [2]

Exploratory: Tables					
No.	Population	IDSL / TST ID / Example Shell	Title	Programming Notes	Deliverable [Priority]
Intradermal Allergen Challenge					
6.5.	All Subjects	EFF_T1	Intradermal Allergen Challenge: Summary Statistics of Mean Diameter Early/Late Phase Wheal/Flare Response by Visit and Treatment/Allergen Strata Combinations	
Include an additional column for Visit (SV, FUV1 and FUV2) between the Shell columns "Treatment" & "N" (group items by treatment then visit) and modify Parameter names as appropriate to the information being displayed; namely "Challenge" and "Negative control" and have additional columns "Item" to capture if its Wheal or Flare and "Phase" to capture Early (15m) or Late (6h).
 
Create two versions of the Table within the output. The 1st uses the Main Treatment descriptors and the 2nd uses the Alternative Treatment descriptors (Pbo P, Pbo U, 20ng P, 20ng U).
	FSP: SAC [2]
6.6.	All Subjects	EFF_T1	Intradermal Allergen Challenge: Summary Statistics of Mean Change from Baseline Diameter Early/Late Phase Wheal/Flare Response by Visit and Treatment/Allergen Strata Combinations	As per main summary table except SV (baseline) visit not included.	FSP: SAC [2]

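### For untransformed responses, the Table 14 note fixes the placebo mean at its posterior median, so the reported probabilities do not match their percentage-change labels

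*SAP*

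**What the plan says.** Table 14 in SAP Section 8.4.2 defines its quantity as "X = Treatment ratio (Active / Placebo) at each planned time point" and labels Item 1, for example, "More than a 90% reduction in mean response relative to Placebo". The text before the table adds: "These posterior probabilities relate to events in the current study, and the mean responses on the treatment arms".

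For a response analysed without transformation, the note under the table says that "the cut-points will be computed using the median of the posterior (adjusted) distribution for Placebo and the above ratios" give the equivalent absolute difference. Its example is: "If Pbo median = 76 then Item 1 would be PP(Difference (A-P) < -68.4".

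The note covers any biomarker left untransformed. It also appears to cover TNSS. SAP Section 9.1.1 models weekly TNSS like the dosing-visit FeNO analysis, "except the response is not anticipated to require any transformation, so the model should be modified to examine differences and not ratios". The FeNO section sets no cut-points of its own, and Table 6.2 in Section 11.13.13 is titled "WM TNSS: Summary of Posterior Distributions and Posterior Probability statements from the Analysis of Weekly WM TNSS data".

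The primary analysis works differently. SAP Section 7.1.2, Step 3, forms percentage attenuation from the parameters in each draw and averages a flag: "Myflag = (pctann > 0); where pctann is the variable storing the Percentage attenuation".

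**The concern.** Write A and P for the model-adjusted active and placebo means and c for the ratio cut-point. The label names the event A/P < c, which for positive P is A − cP < 0. The note evaluates A − P < (c − 1) × median(P). The two expressions have the same centre, but one uses the spread of A − P and the other the spread of A − cP. They coincide only at c = 1.

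A reader of Table 6.2, or of the table for an untransformed biomarker, would take each entry as the probability of the stated percentage change. It is instead the probability of a fixed absolute difference, computed as if the placebo mean were known.

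**Working it through.** **1. The plan's own example.** With placebo median 76 and c = 0.10, the threshold is (0.10 − 1) × 76 = −68.4. This reproduces the SAP figure exactly, so the reading of the note is not in doubt.

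**2. Spread.** Let both arm means have posterior SD s and correlation ρ.

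- Plan: SD(A − P) = s√(2 − 2ρ)
- Labelled event: SD(A − cP) = s√(1 + c² − 2cρ)

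Plan SD divided by the SD that the label needs:

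| c | ρ = 0 | ρ = 0.3 | ρ = 0.5 |
|---|---|---|---|
| 0.10 | 1.41 | 1.21 | 1.05 |
| 0.50 | 1.26 | 1.21 | 1.15 |
| 1.00 | 1.00 | 1.00 | 1.00 |
| 2.00 | 0.63 | 0.61 | 0.58 |

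For example, at c = 0.50 and ρ = 0 the ratio is √2/√1.25 = 1.26. For c < 1 the plan's spread is too wide only while 2 − 2ρ > 1 + c² − 2cρ, that is while ρ < (1 + c)/2. The sign reverses above ρ = 0.55 at c = 0.10 and above ρ = 0.75 at c = 0.50.

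**3. Effect on probabilities.** The documents give no TNSS mean or SD. Assume placebo mean 3, subject SD 2, a posterior ratio of 0.6 (so the active mean is 1.8), independent normal posteriors, and the 20 completers per arm in the Protocol. Then s = 2/√20 = 0.447, SD(A − P) = 0.447 × √2 = 0.632, and the standardised value is (3c − 1.8)/SD.

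| c | 3c − 1.8 | Plan: z, probability | Label: SD(A − cP), z, probability |
|---|---|---|---|
| 0.25 | −1.05 | −1.66, 0.048 | 0.461, −2.28, 0.011 |
| 0.50 | −0.30 | −0.47, 0.318 | 0.500, −0.60, 0.274 |
| 0.75 | 0.45 | 0.71, 0.762 | 0.559, 0.80, 0.790 |
| 0.90 | 0.90 | 1.42, 0.923 | 0.602, 1.50, 0.933 |
| 1.00 | 1.20 | 1.90, 0.971 | 0.632, 1.90, 0.971 |

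The gaps for c below 1 are about 1 to 4 percentage points. The plan's figure is too high where the posterior centre falls short of the cut-point and too low where it passes it. Over a wider assumed range (placebo mean 2 to 4, SD 1.5 to 2.5, ratio 0.6 to 1.0, 20 per arm), the gap is about 0 to 8 points at c = 0.25, 0 to 6 at c = 0.50, 1 to 3 at c = 0.75, and 0 to 6 for a rise above 1.50.

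**4. Which replacement works.** Centre is a random effect. SAP Section 11.9.1 gives it an SD of 1000 where no historical data exist, and Section 9.1.1 names no centre prior for TNSS. Take six centres and the default intercept prior variance of 1E6. The posterior SD of an arm mean evaluated at a centre effect of zero is then about √(1/(6/10⁶ + 1/10⁶)) = 378, so about half of the placebo draws are negative. In the same TNSS illustration at c = 0.75:

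- The plan's form gives about 0.76.
- A flag on the ratio A/P < 0.75 gives about 0.005.
- Flagging A < 0.75P, with the arm means averaged over the sampled centre effects, gives about 0.79, as in the table above.

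**The case against.** The note discloses what it does: it prints the event as a difference, and that is a coherent posterior probability for the event written. This stands. The fault lies in keeping the percentage labels, and relabelling would also cure it.

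The scope is narrow. Biomarkers are log2-transformed by default, and there the ratio is already exact in each draw. The direct-challenge models replace the default comparisons. Table 14 is titled for pharmacodynamic and biomarker analyses, so its use for TNSS is an inference from the FeNO cross-reference and the Table 6.2 title. That also stands.

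A reader might infer three stronger things:

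- **That probabilities of large reductions are always pulled towards 0.5.** This needs ρ below (1 + c)/2. The arms share an intercept and centre effects, so the SAP does not guarantee it.
- **That the errors are typically large.** With independent arms the largest possible error over all posterior positions is about 8 points at c = 0.10, 6 at c = 0.50, 11 at c = 2 and 37 at c = 10. These are maxima, not expected values. If TNSS is a 0 to 12 sum, a tenfold rise needs a placebo mean below 1.2.
- **That the ratio flag of Section 7.1.2 can simply be copied.** Under the default centre SD of 1000 it fails, as step 4 shows.

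**Conclusion.** The point holds as a mismatch between label and calculation. For any response analysed untransformed, every Table 14 item except Items 6 and 7 (any reduction, any increase) reports a probability other than the one it names. Under independent, equally precise arm means the SD is 41% too large at c = 0.10, 26% too large at c = 0.50 and 37% too small at c = 2; other correlations change the sizes and, for reductions, possibly the sign. The 1-to-4-point TNSS differences rest on assumed values.

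The consequence is minor. The affected endpoints are exploratory and no decision threshold is attached to Table 14. The 0.7 success criterion concerns the late asthmatic response endpoints; their attenuation probabilities, and the secondary ones, are computed draw by draw and are not affected.

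**What to change.** Replace the note under Table 14 with:

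> For untransformed responses, in each MCMC draw form the model-adjusted arm means averaged over the sampled effects of the study centres, and flag A < cP (or A > cP) for each Table 14 item; the mean of the flag is the probability.

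Section 9.1.1 should also say whether Table 14 applies to TNSS.

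If the fixed-difference calculation is kept, relabel those items as absolute differences from a stated reference value, not as percentage changes relative to placebo.

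The cost of either is a sentence or two in the SAP and at most a few lines of PROC MCMC code. No new data are needed.

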8.4.2.1 Biomarkers supporting the BAC related exploratory objective(s)

8.4.2.1.1 Sputum

Analyses described in Section 8.4.2.1.1 will use the Sputum producers population. If this population is deemed too small (e.g. less than 3 evaluable subjects per treatment arm/strata combination) a review of each of the planned modelling activities may take place to determine which (if any) of them would be attempted.

Cell Pellet: Sputum Differential cell counts

These analysis models assume all of the required data manipulation steps have been completed and that two response variables are derived per subject; namely a (derived) Total count (in Cells/g sputum – sometimes referred to as Absolute counts in display titles) and a Percentage (% of the Total Non-Squamous Cells). It is expected that a large proportion of subjects may not produce samples and/or viable/evaluable samples at all of the planned timepoints. **Inspection of the amount and pattern of missing data will be conducted, to determine if any form of statistical modelling should take place.** Note: The data manipulation steps add on a small constant in the eventuality that zero counts were recorded for a cell type so there should be no value that cannot be subjected to a log transformation.

Descriptive summary tables will be produced for “%” and Absolute count versions of the endpoints.

Figures of type PD_F1 and PD_F2 should be produced for each combination of response variable (absolute and %) and the cell type (Eosinophils, Neutrophils, etc) using all of the available timepoints.

The most pertinent of the differential cell types are the Eosinophils; although the same modelling process would be attempted for the other cell types (Neutrophils, Lymphocytes, Macrophages, Bronchial Epithelial Cells and Total Non-Squamous cells).

Statistical analysis of “Pre-BAC” Samples

- Additional Figures of type PD_F3
- Separate Bayesian repeated measures mixed effect models (per response variable and cell differential type), with non-informative priors for all model parameters, will be fitted to each transformed response over the planned post Screening time points (FUV1, FUV2 and FUV3).
- Baseline: (Transformed) SV Pre-BAC
- The additional terms to include in the chosen “R” model (see Section 11.9.1) are:
 - Fixed Categorical: Intercept
 - Fixed Continuous Covariates: Baseline*Visit
- The repeated measures term is Visit (Subject = Subject), with an Unstructured variance covariance matrix common to each treatment arm (3x3).

Statistical analysis of “Direct BAC effect” Samples (All Samples)

- Additional Figures of type PD_F4
- Separate Bayesian repeated measures mixed effect models (per response variable and cell differential type), with non-informative priors for all model parameters, will be fitted to each of the transformed responses collected from an individual subject (i.e. 8 data points per subject; the combinations of Visit and Sample times SV Pre-BAC, SV 24 Post BAC, FUV1 Pre-BAC, FUV1 24h Post BAC, FUV2 Pre-BAC, FUV2 24h Post BAC, FUV3 Pre-BAC and FUV3 24h Post BAC).
- For the purposes of assessing models R1 to R3 (see Section 11.9.1) consider “Visit” in those models to be a eight level term covering the data recorded per subject with these additional terms:

Fixed Categorical: Intercept

The repeated measures term is Visit (Subject = Subject), with an Unstructured variance covariance matrix common to each treatment arm (8x8).

- In this model parameterization the usual “Baseline” timepoints (Pre-BACs) are modeled as response variables and not covariates. Therefore posterior distributions for the quantities of interest; namely treatment effect on “within visit fold changes (Post/Pre) adjusted for the screening visit and placebo fold changes”; use fold changes representing the mean predicted response at the timepoint (and not the average of the individual subjects fold changes).

- The model can provide several layers of useful information that should be presented instead of the default set of comparisons. The following should be modified if the model form is “R1”. The Back transformed predicted response for each treatment arm (x2) and visit (x8) combination should be produced. The next stage is to determine the fold change of the predicted response (Predicted Post BAC / Predicted Pre-BAC) within each of the four visits (SV, FUV1, FUV2 and FUV3) for each treatment. For each treatment arm its respective SV fold change can be subtracted from the FUV1, FUV2 and FUV3 visits. This quantity can then be compared across the treatment arms (within each of FUV1, FUV2 and FUV3); to provide an estimate of the screening visit and placebo adjusted change in BAC induced response.

PBS Wash: Allergic Mediators

A similar approach to the analysis of Sputum Differential Cell Counts data will be used for each of the available inflammatory mediators; with the exception being the direction of interest (increases or decreases) may change depending upon which analyte is being modelled (see [Table 13](#) for which direction to prioritise for the biomarker classes).

Cell Pellet RNA

NOT PART OF SAC DELIVERABLE: Conditional on sufficient sample remaining (priority is Cell Pellet and PBS wash data). If available it would produce Affy CHIP data, which would be analysed in a similar fashion to Section [8.4.2.3.4](#).

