- The model can provide several layers of useful information that should be presented instead of the default set of comparisons. The following should be modified if the model form is “R1”. The Back transformed predicted response for each treatment arm (x2) and visit (x6) combination should be produced. The next stage is to determine the fold change of the predicted response (Predicted Post NAC / Predicted Pre-NAC) within each of the three visits (SV, FUV1, and FUV2) for each treatment. For each treatment arm its respective SV fold change can be subtracted from the FUV1 and FUV2 visits. This quantity can then be compared across the treatment arms (within each of FUV1 and FUV2); to provide an estimate of the screening visit and placebo adjusted change in NAC induced response.

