8.4.2.3 Biomarkers supporting the Induction of TLR7 (target engagement) exploratory objective(s)

8.4.2.3.1 Nasal Lavage

- Tables of descriptive summary statistics and Figures of type PD_F1, PD_F2 and PD_F5
- Separate Bayesian repeated measures mixed effect models (per analyte), with non-informative priors for all model parameters, will be fitted to each of the transformed post DV1 baseline responses collected from an individual subject (i.e. 5 data points per subject; the combinations of Visit and Sample times excluding DV1 Pre-Dose; namely DV1 24h Post Dose, DV4 Pre-Dose, DV4 24h Post Dose, DV8 Pre-Dose and DV8 24h Post Dose).
- Baseline: (Transformed) DV1 Pre-Dose
- For the purposes of assessing models R1 to R3 (see Section 11.9.1) consider “Visit” in those models to be the five level effect covering the data recorded per subject (excluding DV1 Pre-Dose) with these additional terms:

Fixed Categorical: Intercept

Fixed Continuous Covariates: Baseline*Visit

The repeated measures term is Visit (Subject = Subject), with an Unstructured variance covariance matrix common to each treatment arm (5x5).

- Only items 6 and 7 from the default set of cut-points (Table 14) should be evaluated for the each of the default within visit treatment comparisons.
- Appropriate combinations of the model parameters should be used to evaluate the following two additional comparisons of interest (all cut point items from Table 14 should be applied to

the posterior distributions obtained for these additional comparisons and also this one:

Posterior Probability the quantity (X) is $\{\text{NOT}[(0.8 \leq X \leq 1.25)]\}$

- 24h response at DV4 vs DV1 for the 20ng GSK2245035 arm (adjusting for equivalent changes on Placebo). This is equivalent to
“[20ng Post at DV4 / 20ng Post at DV1] / [Pbo Post at DV4 / Pbo Post at DV1]”
- Analogous comparison for DV8 Vs DV1
- The above additional comparisons are investigating if there is any evidence for gross amplification or tolerisation of the TLR7 induced responses after 4 and 8 weeks of weekly dosing, using the placebo data to adjust for any drift in the biomarker changes that may be caused by other factors (e.g. seasonal changes in allergen exposure).

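### Direct-challenge biomarker analyses subtract each arm's own screening fold change on the ratio scale, so a chance screening imbalance can distort the contrast, usually with some loss of precision

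*SAP*

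**What the plan says.** SAP 8.4.2.1.1 (sputum, direct BAC effect) fits all of a subject's samples as outcomes. The pre-challenge samples "are modeled as response variables and not covariates", and visit is taken "in those models to be a eight level term covering the data recorded per subject", which includes both screening samples. The mean model is one of R1 to R3 in SAP 11.9.1. Even the simplest, R3, has treatment, visit and their interaction. The intercept is the only fixed term added, so each arm has its own screening means.

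The contrast is then built in this order:

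1. "The Back transformed predicted response for each treatment arm (x2) and visit (x8) combination should be produced"
2. "determine the fold change of the predicted response (Predicted Post BAC / Predicted Pre-BAC) within each of the four visits"
3. "For each treatment arm its respective SV fold change can be subtracted from the FUV1, FUV2 and FUV3 visits"
4. The result is compared between arms.

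SAP 8.4.2.1.4 repeats the rule for FeNO around the bronchial challenge, and SAP 8.4.2.2.1 does so for the nasal challenge: "For each treatment arm its respective SV fold change can be subtracted from the FUV1 and FUV2 visits". Sputum mediators (8.4.2.1.1) and blood cell counts (8.4.2.1.2) follow by reference.

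The SAP works differently elsewhere. SAP 8.4.2 makes log base 2 the default for biomarkers. The pre-BAC analysis of the same sputum data uses the screening value as a covariate. The target-engagement comparison in SAP 8.4.2.3.1 is a ratio of ratios: "20ng Post at DV4 / 20ng Post at DV1] / [Pbo Post at DV4 / Pbo Post at DV1".

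**The concern.** Two separate features matter.

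**Scale.** Data analysed on a log scale describe multiplicative change. Once fold changes are formed on the original scale, subtracting one from another gives a quantity that depends on the arm's screening level. Two arms with the same proportional change then show different results.

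**Free screening means.** Screening samples are taken before randomisation at Dosing Visit 1 (Protocol 7.1.1 and 7.1.2), so the arms share the same expected screening response. Estimating it separately by arm and subtracting it carries any chance imbalance into the treatment contrast.

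At stake is how the BAC and NAC biomarker objectives are read. SAP Table 12 describes success for many of these markers in terms of the Post/Pre ratio. An apparent blunting of the challenge response could reflect screening imbalance, and a real one could be hidden by it.

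**Working it through.** The plan states no power or precision for these analyses, so there is no figure to reproduce. The checks below use the contrast as written.

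**1. Scale.** Let a and p be the screening folds on active and placebo, and let both arms change by the same multiple m. The planned contrast is (ma - a) - (mp - p) = (m - 1)(a - p). It is zero only if m = 1 or a = p. The ratio of ratios is (ma/a)/(mp/p) = 1 always.

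| Screening folds (active, placebo) | m | Planned contrast | Ratio of ratios |
|---|---|---|---|
| 8, 4 | 0.5 | (4 - 8) - (2 - 4) = -2 | 1.00 |
| 2, 3 | 0.5 | (1 - 2) - (1.5 - 3) = +0.5 | 1.00 |
| 2, 3 | 1.5 | (3 - 2) - (4.5 - 3) = -0.5 | 1.00 |

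**2. How likely is the imbalance?** Assume a log2 fold-change SD of 1.0 to 1.5 (not in the documents). The SE of the arm difference is SD x sqrt(2/n).

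- A gap of 1.5-fold or more (log2 = 0.585), in either direction, has probability 6% to 22% at 20 per arm and 19% to 38% at 10.
- A gap of two-fold or more, as in the first row, has probability 0.2% to 3.5% at 20 per arm and 2.5% to 13.6% at 10.

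Twenty completers per arm is the protocol target. Ten is an assumption for sputum, where SAP 8.4.2.1.1 expects many subjects to lack evaluable samples.

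**3. Conditional bias on the log scale.** Let rho be the correlation between screening and follow-up log fold changes (not in the documents). Subtracting a free screening mean leaves a bias of -(1 - rho) times the chance screening difference. If active is 1.5-fold too high at screening with no drug effect, the expected ratio of ratios is 1.5^-(1 - rho): 0.72 at rho 0.2, 0.82 at 0.5 and 0.92 at 0.8. A log scale alone therefore does not remove this part.

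**4. Precision.** Differencing has variance proportional to 2(1 - rho), and adjustment 1 - rho^2. The large-sample ratio is 2/(1 + rho): 1.67 at rho 0.2, 1.33 at 0.5, 1.25 at 0.6 and 1.11 at 0.8. Below rho 0.5, subtraction is noisier than no screening adjustment. The adjustment itself has to be estimated, which reduces the gain. Simulated ratios for log-scale differencing against common screening means are:

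| Subjects per arm | rho 0.2 | rho 0.5 | rho 0.8 |
|---|---|---|---|
| 20 | 1.56 | 1.28 | 1.07 |
| 10 | 1.53 | 1.15 | 0.97 |

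Other runs at 10 per arm gave 1.51 to 1.60 at rho 0.2 and 1.10 to 1.18 at rho 0.6, depending on the form of adjustment.

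**5. False signals with no drug effect.** These come from 4,000 simulated trials per setting with 20 per arm, log2 SD 1.5, pre/post correlation 0.5, screening fold 3 and rho from 0.2 to 0.8. The table gives the chance that the posterior probability of a reduction exceeds 0.95.

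| Situation | As planned | Common screening mean |
|---|---|---|
| All trials | 4.7% to 5.7% | 5.8% to 7.0% |
| Active screening fold more than 1 SE high, m = 1 | 12.8% to 19.0% | 5.9% to 7.7% |
| Same, m = 0.6 | 24.7% to 29.6% | 6.8% to 7.8% |
| Active screening fold more than 1 SE low | 0% to 1.4% | 4.8% to 6.0% |

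The overall rate with a common mean is slightly above 5% (7.8% to 8.8% at 10 per arm) because the simulation treats the estimated covariance as known. The two features separate at rho 0.8 and m = 0.6. Given a high active screening fold, the rate is 25.5% as planned, 10.6% with log-scale subtraction and 6.8% with a common screening mean.

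**The case against.** - **The intended scale may be the log scale.** SAP 8.4.2.1.4 speaks of differences, in place of ratios, only when FeNO is not log-transformed, and on the log scale subtraction is the ratio of ratios. The wording is also permissive. This softens the point, but the written order puts back-transformation and the Post/Pre ratio before the subtraction, and no other screening-adjusted contrast is given.
- **The scale artefact vanishes if m = 1.** SAP Table 15 assumes no underlying change for several of these markers on placebo. That is a planning assumption. Protocol 7.3.1 uses an incremental challenge at screening and a bolus at follow-up, so a common shift around the BAC cannot be excluded.
- **An imbalance would be visible.** Predicted means and within-visit fold changes, including screening, are also to be produced. That helps a careful reader but does not correct the contrast.
- **Screening values as outcomes have a benefit.** The Sputum Producers population (SAP 4) needs only a pre- or a post-challenge screening sample. Missing responses are handled under missing at random, whereas missing covariates are omitted or imputed case by case (SAP 11.6.2.3). This stands, and it argues against using the screening fold change as a covariate here.
- **Table 14.** A reader might infer that its ratio cut-points are misapplied to a difference. They are not: SAP 8.4.2.1.1 presents these outputs in place of the default comparisons. What is missing is any replacement cut-point, although the display list still calls for posterior probability statements (for example Tables 5.5 and 5.21).
- **SAP 8.4.2.3.1.** It does not already contain the needed contrast. It compares two post-dose values with the first pre-dose value as a covariate, so it supports the ratio principle only.

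**Conclusion.** The point holds for the contrast as written. Subtracting fold changes is inconsistent with the log and ratio scale on which these data are modelled. It gives a non-zero result with no drug effect whenever screening folds differ and both arms change by a common multiple other than 1. That part is algebra and needs no assumption.

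The free screening means add a bias conditional on the observed imbalance, in either direction, and usually some loss of precision. The size depends on rho, the SDs and the evaluable numbers, none of which the documents give.

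A reader might infer that the plan inflates false signals overall. It does not: the rate averaged over randomisations is about 5%, because the posterior carries the screening uncertainty. A reader might also take 2/(1 + rho) as the loss to expect. That is a large-sample figure; at 10 per arm the loss is about 1.5 to 1.6 at rho 0.2, 1.1 to 1.2 at 0.6, and little or none at 0.8.

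Only exploratory BAC and NAC biomarkers are affected, and no hypotheses are tested. The primary LAR and secondary EAR models use the screening value as a covariate. The change is worth making before unblinded analysis but does not touch the main conclusion.

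**What to change.** In SAP 8.4.2.1.1, 8.4.2.1.4 and 8.4.2.2.1, and for the sections that follow them by reference:

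1. Form the contrast on the log2 scale and back-transform once, at the end. Report (follow-up Post/Pre divided by screening Post/Pre) on active over the same quantity on placebo.
2. State that the Table 14 ratio cut-points apply to this quantity.
3. Keep the screening values as responses, but constrain the screening Pre and screening Post means to be equal across arms. The screening terms then cancel between arms, leaving an adjusted active/placebo ratio of follow-up fold changes. Subjects with one missing screening sample are retained.
4. Do not use the screening fold change as a covariate where screening samples are missing.

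The cost is SAP wording, a changed contrast and a small change to the mean model and code, because the constraint lies outside R1 to R3 as written. No new data are needed. Step 3 brings little or no precision gain when the sample is very small and the correlation high; steps 1 and 2 are worth making regardless.
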